## 2 INTRODUCTION

This study protocol describes an adaptive Phase 3 multi-center, randomized, placebo-controlled trial of sarilumab for the treatment of severe COVID-19 to assess efficacy in reducing time to alleviation of COVID-19 predefined symptoms and safety in administering an interleukin-6 receptor (IL-6R) blocker during an acute viral pneumonia.

### 2.1 STUDY RATIONALE

As there are no treatments with proven efficacy for treatment of patients with severe or critical COVID-19 in the current SARS-CoV-2 pandemic, investigation of novel or repurposed medication is clearly warranted to minimize the impact of COVID-19 on infected patients and society as a whole.

#### Rationale for Study Design

There are currently no approved treatments for COVID-19. With an increasing amount of people affected by COVID-19 worldwide, it is essential to identify safe treatments quickly. This study utilizes an adaptive phase 3 design aimed at gathering this efficacy data quickly while also closely monitoring safety for all participants. Because the optimal dose regimen of sarilumab IV is unknown for treatment of patients with severe or critical COVID-19, the study includes two dose levels. In addition, a second infusion of sarilumab 200 mg IV, sarilumab 400 mg IV, or placebo can be administered under the conditions specified in [Section 4.1](#). Enrollment to the sarilumab 200 mg IV dose arm will be closed for patients after implementation of Amended Protocol 04 (See [Section 4.3](#)).

As the 2 doses of sarilumab (200 mg IV or 400 mg IV) have not been evaluated formally in a phase 3 clinical trial, the study will have close monitoring by the IDMC. This Phase 3 study utilizes a double-blind to minimize potential for bias on the part of the investigator, patient, or sponsor. Whilst the double-blind is maintained the protocol allows for adaptation of the primary endpoint based on new or emerging information to manage the uncertainties regarding assessment, course and prognosis of pandemic COVID-19.

In the absence of treatments with demonstrated efficacy, a placebo control is warranted to distinguish the safety and tolerability of sarilumab from the background signs and symptoms of COVID-19 infection as well as evaluate its potential to reduce fever, reduce oxygen requirements, and improve clinical outcomes. Due to the severity of COVID-19, in this study 2 patients will be randomized to each sarilumab arm for every 1 patient randomized to placebo in order to minimize the number of patients exposed to placebo.

Because there remains uncertainty regarding appropriate choice of primary endpoint for efficacy trials in hospitalized patients with COVID-19, clinical status represented on a 7-point ordinal scale has been proposed as an endpoint with face-validity and interpretability without regard to the type or target of an investigational treatment. A 7-point ordinal scale clinical assessment has been utilized in a randomized open-label trial of lopinavir-ritonavir in hospitalized adult patients with COVID-19 ([3](#)). In this study ([3](#)) a 7-point ordinal scale with anchors similar to those included in the current protocol did exhibit sensitivity to change over time and results were

reported in sufficient detail to estimate COVID-19 clinical progression over a 14 to 28-day observation period.

A change in 2 points on the 7-point clinical scale included in the current protocol has face validity as a pragmatic measure of clinical status in hospitalized patients with COVID-19 because it is anchored by the intensity of the intervention needed to support respiration.

The key secondary endpoint is percent of patients alive at Day 29, because patients with severe or critical COVID-19 have elevated risk of non-survival related to conditions not captured in the primary endpoint (eg, myocardial infarction, acute kidney injury, coagulopathy, or secondary infection).

## 2.2 BACKGROUND

Coronavirus disease (COVID-19) is caused by severe acute respiratory syndrome coronavirus 2 (SARS-CoV-2), a protein-enveloped RNA virus (4) related to severe acute respiratory syndrome coronavirus (SARS-CoV) and Middle East respiratory syndrome-related coronavirus (MERS-CoV)(5). COVID-19 presents with influenza-like symptoms (fever, cough, dyspnea, nausea, vomiting, diarrhea) and radiographic features of diffuse pneumonia (5, 6, 7, 8, 9), with more severe cases characterized by neutrophilia, lymphopenia, thrombocytopenia, elevations in acute phase reactants and inflammatory cytokines (8), including IL-6 (9). Over 25% of patients develop acute respiratory distress during the second week of hospitalization (7). Acute, life-threatening respiratory injury induced by coronavirus infection is associated with an over-exuberant cytokine release (also known as “cytokine storm”) (10, 11). Case series of patients afflicted with SARS-CoV and MERS-CoV pneumonia indicate that elevations in IL-6 and other pro-inflammatory cytokines are correlated with clinical and radiographic severity (12, 13) and that in SARS-CoV pneumonia, peak viral load precedes peak IL-6 concentration and subsequent peak radiographic severity (14). As of 14 March 2020, there are many efforts to develop vaccines, anti-virals, and therapeutics against COVID-19, but none have yet demonstrated meaningful efficacy.

Clinical management of hospitalized patients with COVID-19 includes supportive therapy: supplemental oxygen therapy to target SpO2, empiric antimicrobials, empiric neuraminidase inhibitor for treatment of influenza when there is local circulation, and intensive care as required (WHO, 2020) (15).

Both SARS-CoV-2 (16, 17) and SARS-CoV (18) exploit angiotensin converting enzyme II (ACE2) to infect pulmonary and intestinal epithelial cells (18, 19, 20) and activate NF-kappa B upregulation of proinflammatory cytokines such as IL-6 (21, 22). SARS-CoV infected pulmonary epithelial cells, pneumocytes, and macrophages (Mφ) produce elevated levels of IL-6, MCP-1, TGF-β1, and other proinflammatory cytokines and chemokines (23).

SARS-CoV infected human bronchial epithelial cells secrete IL-6, IL-8, and gamma interferon (IFN-γ)-inducible protein 10 (IP-10) which stimulates monocyte-derived Mφ and dendritic cells (DC) to also produce, IL-6, IL-8, IL-1β, G-CSF, MIP-1α/β, and TNF-α. These cytokines from SARS-CoV-infected pulmonary epithelial cells interfere with receptor-mediated endocytosis and DC priming of T cells. In vitro anti-IL-6 or anti-IL-8 antibodies restored DC capacity to prime T cells inhibited by cytokines produced by SARS-CoV-infected pulmonary epithelial cells (24). Excessive pulmonary and systemic cytokine release, sustained, in part by IL-6 signaling,

potentially results in infiltration of activated neutrophils into the alveolar space, followed by a fibroproliferative phase characterized by findings of alveolar hyaline membranes, with varying degrees of interstitial fibrosis, and eventual resolution (25, 26, 27).

These findings related to SARS-CoV support the possibility that systemic inhibition of IL-6 signaling can be used to therapeutic advantage when treating COVID-19.

In the setting of infection, IL-6 is an important mediator of fever induction (28). The pyrogenic role of IL-6 was delineated in patients receiving T cell based-immunotherapy (specifically, chimeric antigen receptor-expressing T cells or a CD19/CD3-bispecific antibody) where treatment with the IL-6 receptor antagonist, tocilizumab, quickly reversed the high fevers and other symptoms that developed as part of a cytokine release syndrome (CRS) over several days (29).

During the current COVID-19 outbreak, tocilizumab has been used in 21 patients with severe COVID-19 infection and described in a retrospective study (30). All patients had fever prior to treatment, baseline mean CRP was  $75\pm66.80$ , and mean IL-6 level was  $132\pm278$  pg/mL. One day after treatment with tocilizumab all patients had normal body temperature. Before treatment, 20 of 21 patients required oxygen therapy. After tocilizumab 15 (75%) lowered oxygen intake after treatment and by Day 3 all patients had  $\text{SpO}_2 >94\%$ , including 1 patient who was breathing without supplemental oxygen.

While evidence of efficacy of tocilizumab in COVID-19 remains unproven, early reports suggested that systemic inhibition of IL6 signaling may have value as a supportive therapy.

Sarilumab (KEVZARA®) is a recombinant human IgG1 kappa monoclonal antibody (mAb) directed against soluble and membrane-bound IL-6 receptor (IL-6R $\alpha$ ). Sarilumab, formulated as a solution for subcutaneous (SC) injection at doses of 150 and 200 mg every 2 weeks (q2w), was first approved for the treatment of adult patients with rheumatoid arthritis (RA) in Canada on 12 January 2017, the United States (US) on 22 May 2017, the European Union (EU), Norway, Iceland, and Liechtenstein on 23 June 2017, and Japan on 27 September 2017. Sarilumab is currently approved for the treatment of moderate to severe RA in multiple countries across the globe. Sarilumab inhibition of IL-6 signaling leads to a decrease in concentration of free sIL-6R $\alpha$  and normalization of levels of acute phase proteins and markers of inflammation, such as C-reactive protein (CRP), serum amyloid A (SAA) and fibrinogen (31). Because sarilumab inhibits both soluble and membrane bound forms of IL-6R $\alpha$ , thereby suppressing pro-inflammatory signaling by both pulmonary epithelial and immune cells, it has the potential to reduce the severity of pulmonary COVID-19 complications, including respiratory failure. There is no evidence that sarilumab has anti-viral potential.

## 2.3 BENEFIT/RISK ASSESSMENT

For patients with RA, sarilumab 150 mg and 200 mg every 2 weeks by SC injection has demonstrated clinically meaningful reductions of inflammatory joint swelling and tenderness of RA, improvements in physical function, and reduced progression of joint damage as measured by radiography.

However, in clinical trials of patients with RA sarilumab was associated with an increased risk of infections, including serious infections. As with other immunomodulatory therapies for RA, serious and sometimes fatal infections have been reported on sarilumab.

For this study it is proposed to administer sarilumab IV to patients with a confirmed viral pneumonia for which no antiviral therapy has demonstrated effectiveness. However, the potential benefit of sarilumab for patients with COVID-19 is suppression of the cytokine storm which may be a more important and long-lasting contributor to lung damage than the viral infection itself. One of the features of coronavirus pneumonia is a local and systemic increase in activated neutrophils which function to eliminate the viral infection but also inflict collateral damage to the pulmonary epithelium (26). In this context the dose-related reduction of absolute neutrophil count (ANC) associated with IL-6 $\alpha$  inhibition may help to mitigate the coronavirus-induced neutrophilia.

Uncertainties associated with this study include the route of administration, IV, and the sarilumab 400 mg dose; both intended to increase  $C_{max}$  and decrease  $t_{max}$  compared to SC route. Given that changes in ANC of antibody-mediated sIL-6R $\alpha$  are dose-dependent, irrespective of route of administration, it is anticipated that sarilumab delivered IV will rapidly suppress ANC. Based on analyses of 7985.5 patient-years of sarilumab exposure collected over 7.3 years from 3358 clinical trial patients with RA, the incidence of infection and serious infection did not increase with increasing severity of neutropenia. ANC values on sarilumab were normal for the majority of infections occurring within 12 weeks after sample collection (3452/3943 [88%] and 370/434 [85%] of patients reporting infections from patients treated with sarilumab plus conventional anti-rheumatic disease-modifying drug and sarilumab monotherapy, respectively. Both observations support the consistent finding that low ANC is not associated with an increased rate of infection for patients treated with sarilumab.

To mitigate the uncertainty around safety and tolerability of sarilumab IV, review of safety data by an independent data monitoring committee (IDMC) after the dosing of the first 12 patients will be required.

Although risks of treatment with sarilumab are established and benefits for patients with COVID-19 are potential, the absence of effective treatments of COVID-19 complications associated with excessive cytokine release during this ongoing pandemic, investigations such as this study are warranted.

A recently published retrospective cohort study (n=191) of hospitalized patients with COVID-19 reports that patients with multi-organ dysfunction (MOD), as quantified using the Sequential Organ Failure Assessment (SOFA) score have a 5.65 odds ratio for non-survival (16). Because the potential benefit is marginal relative to the burden of study-related procedures and established risks of sarilumab, patients with multi-organ dysfunction, along with patients who, in the opinion of the investigator are unlikely to survive after 48 hours will not be included in the study.

A risk-benefit statement with respect to the overall development program is provided in the IB and associated addendum.

### 3 OBJECTIVES AND ENDPOINTS

**Table 1 - Objectives**

Primary Objectives

• To evaluate the clinical efficacy of sarilumab relative to the control arm in adult patients hospitalized with severe or critical COVID-19

Secondary Objectives

• Evaluate the 28-day survival rate

• Evaluate the clinical efficacy of sarilumab compared to the control arm by clinical severity

• Evaluate changes in the National Early Warning Score 2 (NEWS2)

• Evaluate the duration of predefined symptoms and signs (if applicable)

• Evaluate the duration of supplemental oxygen dependency (if applicable)

• Evaluate the incidence of new mechanical ventilation use during the study

• Evaluate the duration of new mechanical ventilation use during the Study

• Evaluate the proportion of patients requiring rescue medication during the 28-day period

• Evaluate need for admission into intensive care unit (ICU)

• Evaluate duration of hospitalization (days)

• The secondary safety objectives of the study are to evaluate the safety of sarilumab through hospitalization (up to day 29 if patient is still hospitalized) compared to the control arm as assessed by incidence of:

- Serious adverse events (SAEs)

- major or opportunistic bacterial or fungal infections in patients with grade 4 neutropenia

- Grade <math>\geq 2</math> infusion related reactions

- Grade <math>\geq 2</math> hypersensitivity reactions

- Increase in alanine transaminase (ALT) <math>\geq 3X</math> ULN (for patients with normal baseline) or <math>>3X</math> ULN AND at least 2-fold increase from baseline value (for patients with abnormal baseline)

- major or opportunistic bacterial or fungal infections

Tertiary/exploratory


• Evaluate the virologic changes in the treatment arms compared to the control arm as assessed by nasopharyngeal (NP) and blood quantitative SARS-CoV-2 counts

• To evaluate the cytokine profile and additional biomarkers that may be associated with efficacy and safety associated with sarilumab treatment

• To evaluate the incidence of new or worsening laboratory-confirmed serious secondary infections in the treatment arms as compared to the control arm

• To characterize the concentrations of sarilumab in serum over time

• Patients will not be recalled after discharge for any missing exploratory assessments.

**Table 2 - Endpoints**

**Primary Endpoints**

The primary endpoint is the time to improvement of 2 points in clinical status assessment from baseline using the 7-point ordinal scale.

The 7-point ordinal scale is an assessment of the clinical status. The scale is as follows:

1. Death;
2. Hospitalized, on invasive mechanical ventilation or extracorporeal membrane oxygenation (ECMO);
3. Hospitalized, on non-invasive ventilation or high flow oxygen devices;
4. Hospitalized, requiring supplemental oxygen;
5. Hospitalized, not requiring supplemental oxygen - requiring ongoing medical care (COVID-19 related or otherwise);
6. Hospitalized, not requiring supplemental oxygen - no longer requires ongoing medical care
7. Not hospitalized

**Secondary Endpoints**

**Key Secondary Endpoint**

- Percent of patients alive at Day 29

**Other Secondary Endpoints (Efficacy)**

- Proportion of patients with one point improvement from baseline in clinical status assessment at days 4, 7, 15, 21, 29 using the 7-point ordinal scale
- Mean change in the 7-point ordinal scale from baseline to days 4, 7, 15, 21, 29 (or until discharge)
- Time to resolution of fever defined as body temperature ( $\leq 36.6^{\circ}\text{C}$  [axilla], or  $\leq 37.2^{\circ}\text{C}$  [oral], or  $\leq 37.8^{\circ}\text{C}$  [rectal or tympanic]) for at least 48 hours without antipyretics or until discharge, whichever is sooner
- Time to resolution of fever (as defined above) and improvement in oxygenation (as defined below)
- Days with fever ( $>37.4^{\circ}\text{C}$  [axilla], or  $>38.0^{\circ}\text{C}$  [oral], or  $>38.4^{\circ}\text{C}$  [rectal or tympanic]) based on maximum value observed during a 24-hour period
- Time to change in NEWS2 from baseline
- Time to NEWS2 of  $<2$  and maintained for 24 hours
- Mean change from baseline to days 4, 7, 15, 21, 29 in NEWS2
- Time-to-improvement in oxygenation ( $[\text{SpO}_2]/[\text{FiO}_2]$  of 50 or greater) compared to the nadir for at least 48 hours, or until discharge, whichever is sooner
- Alive off supplemental oxygen at day 29
- Days of hypoxemia ( $\text{SpO}_2 < 93\%$  on room air, or requiring supplemental oxygen, or mechanical ventilatory support)
- Days of supplemental oxygen use
- Days of resting respiratory rate  $>24$  breaths/min (maximum value if recorded at more than once a day)
- Time to oxygen saturation  $\geq 94\%$  on room air
- Ventilator free days in the first 28 days (to day 29)
- Initiation of mechanical ventilation, non-invasive ventilation, or use of high flow nasal cannula (for those not requiring these interventions at baseline)
- Proportion of patients requiring rescue medication during the 28-day period

- ICU status (among those not in an ICU at baseline, record if transferred to the ICU or the need to transfer to the ICU [if the ICU is not available])
- Days of hospitalization among survivors

---

### **Secondary Endpoints (Safety)**

The safety endpoints are:

- Incidence of serious adverse events
- The incidence of major or opportunistic bacterial or fungal infections
- The incidence of major or opportunistic bacterial or fungal infections in patients with grade 4 neutropenia
- The incidence of hypersensitivity reactions, infusion reactions, gastrointestinal perforation
- White cell count, hemoglobin, platelets, creatinine, total bilirubin, ALT on days 1, 4, 7, 15, 21, 29 (if still hospitalized)

---

### **Tertiary/exploratory**

- Evaluate the virologic changes in the treatment arms compared to the control arm as assessed by:
  - Percent of patients with SARS-CoV-2 detectable in nasopharyngeal (NP) sample at days 7, 15, 21, and 29
  - Quantitative SARS-CoV-2 virus in the NP sample at days 7, 15, 21, and 29
  - Development of SARS-CoV-2 variants in NP sample at day 7, 15, 21, and 29
  - Quantitative SARS-CoV-2 virus in blood at days 7, 15, 21, and 29
- To evaluate the cytokine profile and additional biomarkers that may be associated with efficacy and safety associated with sarilumab treatment
- To evaluate the incidence of new or worsening laboratory-confirmed serious secondary infections in the treatment arms as compared to the control arm
- To characterize the concentrations of sarilumab in serum over time
- Patients will not be recalled after discharge for any missing exploratory assessments.

---

## 4 STUDY DESIGN

### 4.1 OVERALL DESIGN

This study is an adaptive phase 3, randomized, double-blind, placebo-controlled trial to evaluate the efficacy and safety of sarilumab in hospitalized adults with severe or critical COVID-19. The study will be conducted in Europe and other countries except in the United States (US) in up to 100 sites.

Patients will be randomized in a 2:2:1 allocation ratio to sarilumab 400 mg IV, sarilumab 200 mg IV, or placebo. The sarilumab 200 mg IV dose arm will be closed for patients enrolled after Amended Protocol 04 is implemented. Patients enrolled after implementation of Amended Protocol 04 will be randomized in a 2:1 allocation ratio to sarilumab 400 mg IV or placebo (Section 4.3). All patients will receive a single dose of study drug on Day 1. Patients may receive a second dose with study drug (based on the original treatment group assigned) 24 to 48 hours after the first dose, if

1. The Benefit Risk assessment by the investigator favors the administration of another dose of study drug without compromising safety (e.g., increase in LFTs, neutropenia)

AND

2. At least one of the following criteria is met:
  - Increase in fever or recurrence of fever compared to Day 1 OR
  - Increase or no change in FiO2 requirement compared to Day 1 OR
  - Requiring vasopressors, ECMO, or development of multi-organ dysfunction

The safety data from approximately the first 12 patients randomized (assuming a total of ~10 patients are dosed on the sarilumab doses of 200 mg IV or 400 mg IV) will be reviewed by an independent data monitoring committee (IDMC) after the last of these patients dosed reaches Day 7. Data on approximately the first 12 and 50 patients (regardless of severity of illness) with at least 7-days follow-up will be reviewed by the IDMC to determine if the study can continue with or without modification. Subsequently, the frequency of IDMC meetings will be determined following the first 2 IDMC meetings. In addition to these specific assessment times, the IDMC will actively monitor interim data to make recommendations about early study closure, changes to study arms, and/or the eligible patient population throughout the course of the study.

Patients will be assessed daily while hospitalized. Discharged patients will be contacted by telephone on Day 29 to assess status and occurrence of re-admission to a hospital. Patients will undergo a series of efficacy, safety and laboratory assessments while in the hospital. Serum IL-6 and other markers will be collected and analyzed in a central laboratory. Nasopharyngeal (NP) samples to monitor viral infection and blood samples will be requested on day 1 (pre-dose), 4, 7, 15, 29 (or up until the day of discharge if the patient is discharged from the hospital before day 29).

Randomization will be stratified by:

- Severity of illness
  - Severe disease
  - Critical disease
- Systemic corticosteroids (Yes/No)

The severity categories are:

- Severe disease:
  - Requires supplemental oxygen administration by nasal cannula, simple face mask, or other similar oxygen delivery device
- Critical disease:
  - Requires supplemental oxygen requiring delivered by non-rebreather mask or high-flow nasal cannula
  - OR Use of invasive or non-invasive ventilation,
  - OR Requiring treatment in an intensive care unit.

Note: Participants meeting criteria for both severity categories will be stratified according to the more severe category.

## 4.2 SCIENTIFIC RATIONALE FOR STUDY DESIGN

### Rationale for Study Design

This Phase 3 study utilizes a double-blind to minimize potential for bias on the part of the investigator, patient, or sponsor. Whilst the double-blind is maintained the protocol allows for adaptation of the primary endpoint based on new or emerging information to manage the uncertainties regarding assessment, course and prognosis of pandemic COVID-19.

Because of the novelty of the SARS-CoV-2 pathogen, the ease with which it spreads within a community, the current absence of effective anti-viral therapies or vaccines, and still evolving knowledge regarding course of disease and risk factors for progression, there is no criterion of efficacy validated by health authorities to support authorization for use. An adaptive design is necessary to accommodate these multiple uncertainties during this global health crisis to make most efficient use of valuable participant data and investigator resources in the context of an ongoing pandemic while maintaining the rigor of a double-blind placebo-controlled comparison.

In the absence of treatments with demonstrated efficacy, a placebo control is warranted to distinguish the safety and tolerability of sarilumab from the background signs and symptoms of COVID-19 infection as well as evaluate its potential to reduce fever, reduce oxygen requirements, and improve clinical outcomes.

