Senior management, who are separate from the blinded team involved in study management and are not involved in any study related activities, reviewed a pre-specified, one time, unblinded interim analysis report ([Section 9.5](#)). Subsequent to this review, a scheduled IDMC reviewed additional unblinded data that is not available to this senior management team ([Section 9.6](#)). Both groups suggested to stop enrollment in the 200 mg arm. Thus, based on anticipation of a more favorable benefit-risk profile in the 400 mg arm versus the 200 mg arm, enrollment in the 200 mg arm will be closed upon implementation of amended protocol 04. The ratio of 2:1 will continue to be maintained for sarilumab 400 mg IV versus placebo after Amended Protocol 04 is implemented.

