## **9.5 INTERIM ANALYSES**

An interim analysis is planned to be performed when approximately 50% of total planned number of patients (~200) are randomized. The efficacy endpoints will be analyzed using the same methods described in the efficacy analyses section ([Section 9.4](#)). The key secondary endpoint will be modified to be the percent of patients alive at Day 15.

The purpose of the interim analyses is to obtain an understanding of the possible drug effect in the population under study. An administrative alpha of 0.001 will be spent at interim analysis ([1](#)). Due to the conservative amount of alpha spent at interim, no alpha adjustment will be made for the primary analysis when the last patient randomized of the whole study reaches Day 29 (or planned Day 29 if the patient is discharged or leaves the study early), or the supportive final analysis at Day 60.

The interim analyses will be performed by an external statistical analysis center and are separated from personnel involved in the trial conduct. The unblinded results can only be viewed by a small group of senior sponsor individuals, who are separate from sponsor personnel involved in the conduct of the study. People involved in the conduct of the study (Patients, Investigators, Study Team, and Project Team) will have no access to the interim analysis results. Sponsor may decide to make changes to the dose and/or alter disease category based on the interim results.

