3 INTERIM ANALYSIS

An interim analysis is planned to be performed when approximately 50% of total planned number of patients (~200) are randomized. The efficacy endpoints will be analyzed using the same methods described in the efficacy analyses section ([Section 2.1.3](#)). The key secondary endpoint will be modified to be the percent of patients alive at Day 15.

The purpose of the interim analyses is to obtain an understanding of the possible drug effect in the population under study. An administrative alpha of 0.001 will be spent at interim analysis. Due to the conservative amount of alpha spent at interim, no alpha adjustment will be made for the primary analysis when the last patient randomized of the whole study reaches Day 29 (or planned Day 29 if the patient is discharged or leaves the study early), or the supportive final analysis at Day 60.

The interim analyses will be performed by an external statistical analysis center which is separate from personnel involved in the trial conduct. The unblinded results can only be viewed by a small group of senior sponsor individuals, who are separate from sponsor personnel involved in the conduct of the study. People involved in the conduct of the study (Patients, Investigators, Study Team, and Project Team) will have no access to the interim analysis results. Sponsor may decide to make changes to the dose and/or alter disease category based on the interim results.

The interim analysis is planned to mainly include the following:

- Demographics and baseline characteristics
- 7-point ordinal scale (observed value and change from baseline category, time to improvement of at least two points, proportion of patients with at least 2-point improvement)
- Patient survival status
- Overview of TEAE
- Number of patients with SAE

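### Amendment 04 leaves the primary endpoint open to adaptation after sponsor management saw unblinded interim results, without limiting who may decide or on what information, so control at 5% is not assured

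*Protocol*

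**What the plan says.** The study-design rationale in Protocol 2.1 and again in 4.2 states: "Whilst the double-blind is maintained the protocol allows for adaptation of the primary endpoint based on new or emerging information". The stated purpose is to manage uncertainty about the course and assessment of COVID-19. Amendment 04 lists both sections among those it changed, and the sentence is still there.

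Protocol 4.3 reports that senior management "reviewed a pre-specified, one time, unblinded interim analysis report". It describes these people as ones "who are separate from the blinded team involved in study management" and not involved in study activities. The IDMC then reviewed further unblinded data that management did not have. The section continues: "Both groups suggested to stop enrollment in the 200 mg arm". Amendment 04 closed that arm.

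SAP section 3 plans the interim report mainly to include the "7-point ordinal scale (observed value and change from baseline category, time to improvement of at least two points", the proportion with at least a 2-point improvement, and "Patient survival status".

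On what may follow the interim, Protocol 9.5 and SAP section 3 both say: "Sponsor may decide to make changes to the dose and/or alter disease category based on the interim results". They keep the results from patients, investigators, the study team and the project team. They spend alpha of 0.001 at the interim and make no adjustment to the primary analysis.

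Protocol 9.4.2 names the primary endpoint. Protocol 9.4.3.1 and SAP 2.4.4.3 put the primary endpoint for 400 mg versus placebo first in a fixed sequence. The SAP has no provision for changing the endpoint.

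**The concern.** An endpoint can be changed mid-trial without cost to the error rate if whoever chooses it knows nothing of the comparative results. The permission in 2.1 and 4.2 does not secure that. Its only condition is that the double-blind is maintained, and the documents support two readings of that phrase. The synopsis describes the study as blinded to participant and investigator, a condition that still holds after management has seen the results. Section 4.2 says the blind also guards against sponsor bias, and part of the sponsor is now unblinded. The text does not say which reading governs.

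The sequence in 9.4.3.1 gives its first test to whatever is the primary endpoint. A replacement would take that place at the full 5%, with no adjustment, on data that include the patients already seen. If the choice leaned towards the outcome that looked better at interim, false claims of benefit would become more likely. Even a well-motivated change would be hard to defend, because the protocol could not show that it was independent of the interim results.

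The possibility is not remote. The amendment history shows that Amendment 02 introduced the present primary endpoint. That was before the interim; a change now would come after it.

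**Working it through.** **1. The plan's own position on alpha.** Inputs from Protocol 9.5 and SAP section 3: 0.001 at the interim, 0.05 two-sided at the primary analysis, no adjustment.
- Upper bound: 0.001 + 0.05 = 0.051.
- Treating the two looks as bivariate normal with correlation √t, where t is the information fraction at interim, overall alpha is 0.0502 at t = 0.5 and 0.0505 at t = 0.3.

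So with the endpoint fixed, the look adds almost nothing, and the plan's reasoning holds.

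**2. What the text permits.**

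| Question | Sections 2.1 and 4.2 | Section 9.5 and SAP section 3 |
|---|---|---|
| What may change? | Primary endpoint | Dose, disease category |
| On what information? | New or emerging; source not limited | Interim results |
| Who decides? | Not stated | Sponsor |
| Until when? | While the double-blind holds | Not stated |

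Section 9.5 does not say its list is exhaustive and does not refer to the permission in 2.1 and 4.2. No section bars people who have seen the results from proposing or approving an endpoint change.

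**3. Information fraction for 400 mg versus placebo.** The documents give no figure, so a range is needed.
- About 200 patients at 2:2:1 give 80 + 40 = 120 in this comparison.
- If the other 200 were all randomized 2:1, they add 133 + 67 = 200. Then t = 120/320 = 0.375 by patient count.
- If 2:2:1 had continued throughout, the final comparison would be 160 + 80 = 240. Then t = 120/240 = 0.5.
- The interim is triggered by randomization, with no follow-up requirement, so information in events may be lower. I take 0.2 as a low value.

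**4. Effect of an interim-driven choice between two endpoints.** Assumptions: no treatment effect on either endpoint; correlation ρ between their Z statistics; the endpoint with the larger interim Z is chosen and tested on all data. Write A₁ and A₂ for the interim Z values and F₁ for the final Z of endpoint 1. By symmetry,

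P(false claim of benefit) = 2 × P(F₁ > 1.96 and A₁ > A₂),

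where F₁ and A₁ − A₂ have correlation √(t(1 − ρ)/2). If the choice is unrelated to the interim, that correlation is 0 and the result is 2 × 0.025 × 0.5 = 2.5%. Otherwise:

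| t | ρ = 0.3 | ρ = 0.5 | ρ = 0.7 |
|---|---|---|---|
| 0.2 | 3.69% | 3.52% | 3.30% |
| 0.375 | 4.08% | 3.86% | 3.58% |
| 0.5 | 4.28% | 4.05% | 3.73% |

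Example: t = 0.5 and ρ = 0.5 give correlation √(0.5 × 0.5/2) = 0.354 and a probability of 4.05%. Simulation with 4 million runs per cell agrees to within 0.02 percentage points.

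**5. What this measures.** The inflation is on the benefit side. Under this rule the two-sided rejection rate stays near 5.0%, because false findings of harm fall as false findings of benefit rise. If the endpoint with the larger absolute Z were chosen instead, the two-sided rate at t = 0.5 would be 7.3% to 8.0% for ρ from 0.7 to 0.3. With three candidates and the larger signed Z at t = 0.5, false claims of benefit would be 4.6% to 5.7% over the same correlations.

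**The case against.** The best defence is that the documents, read together, already confine the risk. Section 9.5 says what may change on interim results, and the endpoint is not there; Amendment 03 added that text to specify the type of modification. The unblinded managers are described as separate from the trial team. The disputed sentence is rationale, not procedure, and is conditional on the blind. The endpoint and the testing order are specified in both documents. Any change would need an amendment with ethics approval. Closing the 200 mg arm is weak evidence of wider influence: it is a dose change, which 9.5 allows, and the IDMC suggested it too. Finally, SAP section 3 says only what the report was planned mainly to contain, not what management actually saw.

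Most of this stands. A reader might infer that the protocol authorises an endpoint switch on the interim results, or that the 5% level is already lost. Neither is supported. Section 9.5 gives no such authority, and a choice made without knowledge of the results costs nothing.

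What remains is narrower. The list in 9.5 is permissive and does not close the separate permission in 2.1 and 4.2. The firewall governs who sees results, not who may propose or approve an endpoint change. Ethics approval is not a control on type I error. The arm closure does show that suggestions from the unblinded group can lead to an amendment.

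**Conclusion.** The concern holds in a limited form. An open permission to adapt the primary endpoint survives in the current protocol after a sponsor-viewed unblinded interim, with no cut-off, no named blinded decision-maker and no exclusion of trial data. Control at 5% is therefore not assured, which is different from saying that it has been lost.

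The size is conditional. If knowledge of the interim results influenced a choice between two endpoints, false claims of benefit would rise from 2.5% to roughly 3.3% to 4.3%. The correlations, information fractions and selection rule behind that range are assumptions; the documents give none of them. It is not the error rate of the plan as written. The finding itself rests on the wording and needs no particular value in the range. It is worth acting on because the permission is explicit and closing it costs almost nothing.

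**What to change.** Delete the sentence in Protocol 2.1 and 4.2. In its place state that the primary and key secondary endpoints, and their testing order, are fixed as of the unblinded interim review.

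If the sponsor wants to keep some room, a total freeze is broader than needed. The alternative is to allow a later change only when all of these hold:
- it is decided by personnel blinded to the interim results;
- it rests solely on information from outside the trial;
- it is documented, with date and reasons, before database lock.

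Under either version, any other outcome proposed later is supplementary and outside the hierarchy. Repeat the rule in Protocol 9.5 and SAP section 3, so that the list of permitted changes and the endpoint rule are read together.

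The cost is a few sentences in the next amendment and a matching SAP update. The sponsor gives up some flexibility to change the endpoint; under the alternative version it keeps the part that can be exercised without cost to the type I error.
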